PROTOCOL TITLE: Topiramate for infants receiving whole body cooling in neonatal encephalopathy

NCT01765218

Document Submission Date to IRB 6/6/2018

Last IRB Review of Study 3/28/2023

PROTOCOL TITLE: Topiramate for infants receiving whole body cooling in neonatal encephalopathy

1) Protocol Title

Title: Topiramate for infants receiving whole body cooling in neonatal encephalopathy

Protocol Version Date: May 25th, 2018

2) Objectives

- a) Specific Aims: To determine the effect of adjuvant topiramate treatment on the outcome of newborns with perinatal depression (including neonatal encephalopathy) who are already receiving the therapeutic whole body cooling.
- b) Hypotheses: We hypothesize that adjuvant therapy with topiramate will reduce short term disease severity in infants with neonatal encephalopathy/perinatal depression who are receiving whole body cooling. Specifically, we hypothesize that adjuvant topiramate will reduce the incidence of seizures (the primary outcome) in these infants. Secondary objectives include assessing the effect of that adjuvant topiramate in infants with neonatal encephalopathy/perinatal depression on biochemical markers of neuronal damage (serum UCHL1/ urine S100 β levels), a composite score of aEEG/cEEG abnormality, and on developmental outcomes at 9m, 18m and 27m.
- c) Scientific Problem: Neonatal encephalopathy is a devastating and unexpected disease in newborns that affects 1.5 to 2.6 per 1000 live births (Kurinczuk 2010). Neonatal encephalopathy has a mortality rate of up to 30% and survivors are at significant risk for adverse outcomes, including seizures, cerebral palsy, and neurodevelopmental delay. Until recently, only supportive care could be offered to these infants, and no therapy was available to modify the natural history of the disease. However, therapeutic hypothermia, or whole body cooling, has been shown to be beneficial for these infants. Hypothermia reduces mortality and decreases the risk of moderate to severe handicap in survivors. (Shankaran 2005).

Although whole body cooling is effective at reducing the mortality and morbidity of neonatal encephalopathy/perinatal depression, the long-term outcome for such babies remains poor. For example in a recent NICHD funded study, whole body cooling reduced the rate of death but had no significant effect on long-term neurodevelopmental outcome of the survivors or moderate or severe disability from 62% to 44% (Shankaran 2012).

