Infants assigned to the topiramate group will receive 5mg/kg of topiramate daily enterally for a total of 5 doses. This is the minimum therapeutic dose of topiramate for infants. The first dose will be administered on the day of enrollment and will continue through and after rewarming. The duration of drug administration was chosen to encompass the cooling period as well as a brief period after rewarming is complete as this is a period where some infants develop seizures and display more signs of neurological damage. The control group will receive a placebo instead of topiramate. Pharmacy will prepare and send to NICU the placebo or study drug solutions in a way to be similar in appearance and volume. Initiation of cooling will not be delayed, but families will be approached for consent as soon as possible after cooling has started.

The cooling protocol includes a range of laboratory evaluations which will be carried out irrespective of whether the patient is enrolled in the study. These include: complete blood count, PTT/INR, DIC panel, complete metabolic panel, ammonia, lactate, troponin-I, CK panel, blood gas, and urinalysis at the initiation of cooling and then every 24h until rewarming is complete (unless the Attending Neonatologist decides that more frequent or less reassessments are needed clinically). Blood gases, blood glucose and ionized calcium levels are measured at the initiation of cooling and then every 6h until rewarming is complete. Once labs have normalized per the discretion of the covering Attending some of these labs may be discontinued. These lab values will provide important data of the severity of each infant's hypoxic-ischemic insult and for patient safety monitoring including information on liver function, kidney function, ammonia toxicity, metabolic status, and acidosis. Enrollment in the study will not change the frequency of these assessments.

A single channel EEG recording (an amplitude EEG, aEEG) or continuous video EEG is recorded continuously on all patients until rewarming is complete. This method measures the degree of encephalopathy and detects seizures.

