The Pediatric Neurology service is by protocol consulted on all cooling patients. They will evaluate the infant and determine a neonatal encephalopathy score daily under the supervision of our Pediatric Neurologists. The presence of clinical seizures will be noted based on review of the bedside aEEG or cEEG. The aEEG/cEEG data will be reviewed in 3 hour increments and document the time when the voltages on the aEEG/cEEG first return to normal. The aEEG/cEEG is used throughout the cooling phase and is generally discontinued after rewarming is completed but may be continued longer for abnormal tracings such as seizures at the discretion of the Neonatology Attending. In addition, the Attending Pediatric Neurologist will assess quality of movements, posture, reflexes, and muscular tone, each infant's neurologic status will be categorized as normal (completely normal neurologic status), unspecific signs (eg, asymmetric muscle tone or reflexes) or abnormal with lack of reflexes and bilateral muscular hypotonia or hypertonia.

Additional tests in infants enrolled in this research study include: serum UCHL1 and urine levels of S100 β , both will be measured at enrollment, at the start of rewarming, and at one-week of life. Topiramate trough drug levels will be collected 24 hours after the first, third, and fifth doses. The drug levels will be run by the UCDMC laboratory. These

PROTOCOL TITLE: Topiramate for infants receiving whole body cooling in neonatal encephalopathy

are the only additional laboratory assessment that study infants will receive as a result of taking part in the study.

All infants on the cooling protocol, irrespective of the research study, will have an MRI with spectroscopy on day 5-7 of life. For this study, these images will be read by a single radiologist, our collaborator [name] of Neuroradiology. The reporting of MRI and MRS results will be standardized in conjunction with [name] to create a more consistent scoring method.

Following discharge, each infant will receive long-term developmental follow-up through the MIND clinic our High Risk Infant follow-up clinic. Infants will be seen at approximately 9, 18, and 27 months. The infants will have standardized Bayley Scale of Infant Development (BSID) III neurodevelopmental screening at these clinic follow-ups supervised by [name].

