The BSID-III contains 3 domains: cognitive, language (receptive and expressive communication), and motor (fine and gross motor). The cognitive scale includes items that assess sensory perceptual development, exploration and manipulation, object relatedness, concept formation, memory, and other aspects of cognitive processing. To allow comparison of results from the 3 domains, a composite score is calculated for each domain (mean, 100). A composite score below -2 SD (<70) is considered a severe delay for all domains. A Pediatrician will assess the quality of movements, posture, reflexes, and muscular tone at each clinic visit. Each infant's neurologic status will be categorized as normal gait and walking, unspecific neurological signs (eg, asymmetric muscle tone or reflexes, muscular hypotonia), or abnormal with upper and/or lower extremities muscular hypertonia (signs of cerebral palsy (CP) present).

9) Data and/or Specimen Management and Confidentiality

Power Calculation

Our primary hypothesis is that topiramate will reduce the frequency of early seizures (i.e. before hospital discharge). From our current data, 64% of infants have seizures prior to hospital discharge; a sample size of 42 will have an 80% chance of detecting a reduction of seizure rate by 2/3 with a p-value of 0.05.

Statistical Methods

Our primary outcome is that seizures before hospital discharge will be significantly reduced in the topiramate group compared to the controls. This will be assessed by nominal logistic regression with the presence or absence of seizures as the nominal dependent variable, and treatment group (topiramate or control) as an independent variable. Other independent variables will include those that are unbalanced between the treatment groups at randomization, and factors that could affect the risk of seizures (these would include neonatal encephalopathy score at study entry, time to initiation of cooling (< or \geq 3h), gender etc).

The effect of treatment assignment on neonatal encephalopathy score (measured daily) will be assessed by repeated measures ANOVA with neonatal encephalopathy score as the dependent variable, time and treatment assignment as the independent variable, and addition independent variables included as appropriate (see above). Time to normalization of aEEG/cEEG in the two different groups will be assessed by Kaplan-

PROTOCOL TITLE: Topiramate for infants receiving whole body cooling in neonatal encephalopathy

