Meier analysis. The effect of treatment on S100 β levels in the urine or UHCL1 in the blood and on other markers of tissue injury will be compared using ANOVA (for outcomes measured once) and by repeated measures ANOVA for those measured on more than one occasion, at predetermined times.

Effect of treatment assignment of development assessments will be assessed individually at the 9m, 18m and 27m examinations.

All tests will be considered significant at $p<0.05$. Where necessary, Tukey-Kramer's test will be used to account for multiple comparisons

Data Specimen/Management

Data specimens will be stored in the NICU and numerically coded, only those who are involved with this study will have access to the specimens. The specimens will only be stored for the duration of the study and thereafter discarded.

10) Data and/or Specimen Banking

There is no plan for specimen or tissue banking in the future.

11) Provisions to Monitor the Data to Ensure the Safety of Subjects

To monitor the safety of each newborn we will track the following variables closely during the intervention: blood gases, blood pressure (hypotensive episodes and required interventions), evidence of seizure activity, and serum topiramate levels. This study is only applicable to newborns with neonatal encephalopathy admitted to the NICU at UC Davis for cooling therapy. Neonatal encephalopathy is a life threatening disease with 30% chance of death and 64% chance of seizures during the neonatal period. These patients receive 24 hours daily continuous extremely close physiological and biochemical monitoring based on their underlying disease state.

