Babies will be ineligible if they have major congenital abnormalities. If the baby had a proven (i.e. electrically confirmed seizure) prior to enrollment they would not be eligible for the study. If a seizure occurred after enrollment/ randomization but before the first dose of study medication the protocol would continue based on the intention to treat. Treatment of seizures will be guided by our Pediatric Neurologists (who will be unaware of treatment assignment). Currently we do not use topiramate for treatment of seizures, and do not intend to change our management of seizures in the foreseeable future. Our first line treatment is phenobarbital, second line is levetiracetam, and the third line treatment is ativan. So, any baby who developed seizures during the protocol would receive our current standard of care, but continue to be in the study. The study protocol will not change the management of seizures should they occur. Once enrolled, a baby would not be withdrawn because of seizures (irrespective of number). We would manage these seizures according to our current clinical practice (see above). Although our primary endpoint (seizures) has been met, we would continue to collect data on secondary endpoints and on safety measures. Patients with renal deficiency (creatinine >2 mg/dL) and liver failure (ammonia >100 mcmol/L) will not be eligible for the study.

13) Risks to Subjects

Newborns with neonatal encephalopathy are very vulnerable. Given the high risk of lifelong neurologic injury and the low risk of the proposed intervention, the risk to benefit ratio of this study is reasonable. Every effort will be made to ensure that the infants receive excellent care and that the parents of the infants fully understand the benefit/risk of the study. Topiramate has been extensively used to treat variety of neurological diseases including seizures in adults, children, and infants. It is a widely used drug with minimal side effects. In adults, topiramate can cause side effects not likely to be obvious in neonates (e.g. paresthesias, dizziness, fatigue, drowsiness, depression, coordination problems, nausea, and difficulty concentrating). These should not be a problem in study infants as babies who receive whole body cooling are routinely sedated with morphine, and any additional sedative effect from topiramate is likely to be minor. Babies who receive whole body cooling are NPO so the possible side effect of nausea by topiramate should be minimized.

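### UCHL1 and S100β: the repeated-measures ANOVA does not separate the enrolment value from the later outcomes and names no baseline covariate

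*Combined protocol and SAP*

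**What the plan says.** Section 2 (Objectives) makes "biochemical markers of neuronal damage (serum UCHL1/ urine S100 β levels") a secondary objective. Section 8 (Procedures Involved) gives the sampling times: "both will be measured at enrollment, at the start of rewarming, and at one-week of life".

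Section 9 (Statistical Methods) gives the analysis. Markers measured once are compared by ANOVA, the others "by repeated measures ANOVA for those measured on more than one occasion, at predetermined times". No model terms, outcome visits or covariates are listed for the biomarkers.

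The same section gives more detail for the daily encephalopathy score, also analysed by repeated measures ANOVA: "time and treatment assignment as the independent variable, and addition independent variables included as appropriate (see above"). That reference leads back to the seizure model, where "Other independent variables will include those that are unbalanced between the treatment groups at randomization", together with factors that could affect seizure risk. The section also sets significance at 0.05 for all tests and provides Tukey-Kramer for multiple comparisons where necessary.

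On timing, section 8 says "The first dose will be administered on the day of enrollment". Section 12 (Withdrawal of Subjects) considers a seizure occurring "after enrollment/ randomization but before the first dose of study medication". Enrolment therefore precedes dosing, and the enrolment sample is probably pre-dose, but no section times the sample itself against the dose.

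**The concern.** A value taken before treatment cannot carry a treatment effect. Kept among the outcomes, it dilutes a group main effect; used as a covariate, it removes between-infant variation. The wording does not choose between these uses. It fits at least four unadjusted tests: the group main effect over three visits, treatment-by-time, baseline-versus-post, and the group effect over the two later visits.

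With 21 infants per arm, precision on these secondary markers is scarce and the enrolment sample is already planned. At stake are the power of the biomarker comparison and an unambiguous statement of what it tests.

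**Working it through.** **No plan figure to reproduce.** The documents give no SD, correlation, effect size or power for either biomarker. The sample size of 42 was set for seizures and does not bear on this point.

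**Inputs.** From the documents: 21 per arm, three samples, alpha 0.05. Assumed: two-sided tests, unit SD at each visit, equal correlation ρ between visits, a pre-dose enrolment sample, and arm differences (0, d1, d2) at the three visits. Write m = (d1 + d2)/2.

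**Effect and per-infant variance V of each contrast**
- Main effect over three visits: (d1 + d2)/3 = 2m/3; V = (1 + 2ρ)/3
- Baseline-versus-post: m; V = (1 + ρ)/2 + 1 − 2ρ
- Later values only: m; V = (1 + ρ)/2
- Later values adjusted for enrolment: m; V = (1 + ρ)/2 − ρ²

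Power uses the noncentral t with noncentrality effect/√(2V/21), on 40 df (39 adjusted). Treatment-by-time uses the noncentral F on 2 and 80 df, with λ = (21/2) × Σ(δ − mean δ)²/(1 − ρ), where δ runs over the three arm differences.

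**Precision, whatever the effect pattern.** For the averaged contrast, the adjusted variance is smaller than the later-values variance by ρ². It is smaller than the baseline-versus-post variance by 1 − 2ρ + ρ² = (1 − ρ)². Neither difference can be negative. At a single visit the variances are 1 unadjusted, 2 − 2ρ for change and 1 − ρ² adjusted, and the differences are again ρ² and (1 − ρ)².

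**Example at ρ = 0.5, d1 = d2 = 0.8**
- Main effect: 1.6/3 = 0.533, V = 0.667, noncentrality 2.12, power 54%
- Baseline-versus-post: V = 0.75 + 1 − 1 = 0.75, noncentrality 2.99, power 83%
- Later values only: V = 0.75, noncentrality 2.99, power 83%
- Adjusted: V = 0.75 − 0.25 = 0.50, noncentrality 3.67, power 95%

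**Power, 0.8 SD at both later visits**

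| Test | ρ = 0.3 | ρ = 0.5 | ρ = 0.7 |
|---|---|---|---|
| Main effect, three visits | 64% | 54% | 47% |
| Treatment-by-time | 60% | 75% | 93% |
| Baseline-versus-post | 69% | 83% | 96% |
| Later values only | 88% | 83% | 78% |
| Adjusted average | 92% | 95% | 99% |

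The gain over the best unadjusted test is about 4, 12 and 2 points; at ρ = 0.1 it is about 0. For 0.8 SD tested at a single visit, power is 75, 83 and 94% adjusted against 72% unadjusted.

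**Where the averaged contrast loses.** Take 0.8 then 0.2 SD, so m = 0.5. The mean δ is 0.333 and Σ(δ − mean δ)² = 0.111 + 0.218 + 0.018 = 0.347. At ρ = 0.5, λ = 10.5 × 0.347/0.5 = 7.28. Treatment-by-time then has 66% power against 61% for the adjusted average; at ρ = 0.7 it is 87 against 75%. With 0.8 SD at one later visit only, it is 60, 75 and 93% against 39, 43 and 56% at ρ = 0.3, 0.5 and 0.7.

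**Sensitivity.** With correlation decaying over time (ρ, then ρ²), best unadjusted against adjusted is 88 v 89, 84 v 89 and 88 v 94%. If 20% of enrolment samples were missing at random (assumed), the adjusted test has 84, 87 and 95% when those infants are dropped, and 90, 92 and 95% with pooled-mean imputation. In a 20,000-run simulation each test, fixed in advance, rejected in 4.8 to 5.3% of runs under the null.

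**The case against.** **The encephalopathy-score wording may carry over.** The method is the same and the sentences are close together, so this is a fair reading, though not a compelled one. A reader might infer that the plan rules out baseline adjustment; the documents do not support that, because they are silent. But even if carried over, the rule would bring in the enrolment value only if it were found unbalanced. That depends on the data and is not a pre-specified covariate.

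**The averaged contrast is not always best.** This stands. A reader of the table might infer that the adjusted average beats every alternative unless the effect is confined to one visit. It already loses to treatment-by-time when the effect is mostly at one visit. The schedule makes a fading effect plausible: five daily doses start on the day of enrolment, so the one-week sample falls after the last dose and the rewarming sample falls during dosing. The choice of contrast is a trade-off for the sponsor.

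**An open choice of test could affect error control.** A reader might infer that Type I error is inflated. Each test fixed in advance holds its level. Reporting whichever of the four unadjusted tests is significant would give about 13% in simulation, but nothing in the documents says this would be done. It is a reason to name the contrast, not evidence of inflation.

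**The gains are assumed and multiplicity is already covered.** Both stand. The correlation and effect size are not in the documents, the gain over the best unadjusted test can be close to nil, and Tukey-Kramer is available.

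**Conclusion.** The point holds as a minor one. The biomarker analysis, unadjusted as written, does not separate the enrolment value from the outcomes and does not pre-specify it as a covariate. Adjustment is at least as precise for any given later-visit contrast, apart from one or two degrees of freedom, provided the enrolment sample is pre-dose. The size of the gain depends on the assumed correlation and effect.

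The dilution to two-thirds applies only if enrolment is pre-dose, counted as an outcome, and the main effect is tested. A reader might take that as the planned analysis, but the documents do not say so. Nothing here touches the primary seizure analysis or the sample size.

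**What to change.** In section 9, state that the start-of-rewarming and one-week UCHL1 and S100β values are the outcomes, and that the model contains treatment, visit, treatment-by-visit, the enrolment value and its interaction with visit. Name the treatment contrast in advance: the average over the two visits, a joint test, or visit-specific effects using the existing Tukey-Kramer provision. Which one is the sponsor's choice.

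In section 8, add a line that the enrolment sample is taken before the first dose of study medication. Say how infants without an enrolment sample are kept in, for example by a constrained baseline model or imputation from the pooled enrolment mean.

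The cost is wording, one or two degrees of freedom, and a rule for missing enrolment samples. No new samples are needed.

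### Routine injury labs may be stopped once normal but are analysed by repeated-measures ANOVA, which discards recovered infants, more of them in the faster-recovering arm

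*Combined protocol and SAP*

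**What the plan says.** Section 9, Statistical Methods, names ANOVA for injury markers measured once. Repeated markers are compared "by repeated measures ANOVA for those measured on more than one occasion, at predetermined times". The sentence covers urine S100β, blood UCHL1 and further tissue-injury markers that it does not list. It states no rule for missing values and no contrast.

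Section 8, Procedures Involved, sets the routine panel at the start of cooling and every 24 h until rewarming is complete. The panel includes "ammonia, lactate, troponin-I, CK panel, blood gas, and urinalysis at the initiation of cooling". Two clauses loosen that schedule:

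- The interval holds "unless the Attending Neonatologist decides that more frequent or less reassessments are needed clinically".
- "Once labs have normalized per the discretion of the covering Attending some of these labs may be discontinued".

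Section 8 adds that enrolment does not alter how often these labs are taken, and that UCHL1, S100β and topiramate levels are the only extra laboratory tests. UCHL1 and S100β have three set times: enrolment, start of rewarming and one week of life.

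**The concern.** The analysis presumes values at fixed times, while the procedures allow a series to end because the marker has become normal. The outcome itself then causes the gaps. Classical repeated-measures ANOVA needs a full series per infant, so it keeps mainly infants whose marker stayed abnormal. If topiramate speeds recovery, more topiramate infants are removed. Blinding does not prevent this, because the attending physician reacts to the lab value and not to the allocation.

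At stake is a real benefit on these secondary markers being understated or missed. With 21 infants per arm there is little room for dropping incomplete series.

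**Working it through.** **The plan's own figure.** The only sample-size figure is for seizures (Section 9, Power Calculation): 42 infants, 80% power, 64% reduced by 2/3 to 21.3%. Taking a two-sided 5% level without continuity correction, n per arm = [1.96·√(2·0.427·0.573) + 0.842·√(0.64·0.36 + 0.213·0.787)]² / 0.427² = (1.371 + 0.531)² / 0.182 ≈ 19.9, so 20 per arm and 40 in total. This is close to 42 and does not depend on the labs. No figure is given for any marker.

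**Which markers are exposed.** S100β and UCHL1 have set times and are not in the routine panel. Since only drug levels are added besides these two, any other repeated laboratory marker must come from the panel that may be stopped.

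**Assumed inputs (none is in the documents except 21 per arm).** Samples at 0, 24, 48 and 72 h. The log marker starts 0.8 to 1.6 above the normal limit, with SD 0.8 between infants. It falls 0.45/day on control and 0.65/day on topiramate. Slope SD is 0.1 and residual SD 0.3. After a normal value the lab stops with probability 0.5 to 1.

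**Two contrasts, kept apart.** Both use power ≈ Φ(|difference|/SE − 1.96).

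- Time-averaged difference: −0.20 × (0+1+2+3)/4 = −0.30. SD of an infant's mean = √(0.8² + (1.5·0.1)² + 0.3²/4) = 0.828. SE = 0.828·√(2/21) = 0.255. Power with full data ≈ Φ(1.17 − 1.96) ≈ 21% (simulation: about 20%).
- Change to 72 h: −0.20 × 3 = −0.60. SD of change = √((3·0.1)² + 2·0.3²) = 0.520. SE = 0.160. Power with full data ≈ Φ(3.74 − 1.96) ≈ 96% (simulation: about 95%).

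**Complete cases.** In simulation (at least 1,000 trials per setting), about 45-87% of controls and 28-78% of topiramate infants have a complete series.

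| Contrast | Full data | Complete cases, stop 0.5 | Complete cases, stop 1 |
|---|---|---|---|
| Time-averaged difference | about −0.30 | −0.23 to −0.26 | −0.05 to −0.13 |

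The change to 72 h stays at −0.58 to −0.61 over stop probabilities 0.5 to 1, and its power falls to about 48-88%.

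The average shrinks mainly because the retained topiramate infants start higher than the retained controls (gap +0.05 to +0.22). The change to 72 h subtracts that start. Its power loss follows from numbers alone:

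- Fewest retained: 0.45·21 = 9.45 and 0.28·21 = 5.88 infants. SE = 0.520·√(1/9.45 + 1/5.88) = 0.273. Power ≈ Φ(2.20 − 1.96) ≈ 59%. Simulation gives about 48%, since a t-test on so few infants does worse than the normal approximation.
- Most retained: 18.27 and 16.38 infants. SE = 0.177. Power ≈ Φ(3.39 − 1.96) ≈ 92% (simulation: about 88%).

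With slope SD 0.15 the power for change starts at about 87% and falls to 35-77%. The estimate is then −0.54 at worst.

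**A second set of assumptions.** Here there is an extra sample at 84 h, the start is 1.0 to 2.0 above the limit, and the extra decline is 0.2 or 0.4/day. The time-averaged effect shrank in 17 of 18 scenarios with a true benefit. At 25% stopping, 87-98% of it was kept in five of six scenarios and 105% in the sixth. Its power at 0.4/day still fell from about 80% to 62-67%. With no true effect, false-positive rates stayed at about 4-6%.

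**Alternatives.** A random-slope mixed model on all recorded values gave slope differences of −0.198 and −0.196 against a true −0.200. In the first setting its power for the 72 h change was about 75-97%, from only 60 trials per setting. Carrying the last normal value forward gave a 72 h change of −0.24 to −0.50 against −0.60, with power 18-79%.

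**The case against.** The unnamed markers are never defined. Section 8 presents the routine labs as severity and safety data ("These lab values will provide important data of the severity of each infant's hypoxic-ischemic insult"), and the secondary objectives in Section 2 name only UCHL1 and S100β. This stands as a limit: the exposed endpoints are inferred. But Section 9 does add further markers, and Section 8 leaves no other laboratory source for a repeated one.

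Section 8 says only that some labs may be stopped, and Section 9 does not say that incomplete series are deleted. Both points are fair. The large losses need near-certain stopping. Deletion is what the classical method does when nothing else is specified, and nothing else is.

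Three stronger readings are tempting, and the material does not support them:

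- *That high power is lost because the effect shrinks towards zero.* The contrast that shrinks had only about 20% power with full data. The well-powered contrast, change to 72 h, is nearly unbiased and loses power through fewer infants.
- *That the encephalopathy score has the same weakness.* Section 9 says "The effect of treatment assignment on neonatal encephalopathy score (measured daily) will be assessed by repeated measures ANOVA". The stop-when-normal clause covers only labs, and no text ends scoring on recovery. The lack of a stated last day is a separate matter.
- *That the main results are threatened.* Seizures, S100β and UCHL1 are not subject to the clause.

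**Conclusion.** The conflict between Sections 8 and 9 is in the text, and the method named handles it badly. Its direction is clear for the time-averaged comparison: a real benefit is understated. For change to 72 h the cost is power, not bias. False-positive rates were not raised.

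The size cannot be known from the documents. It runs from small shrinkage at 25% stopping to loss of most of the time-averaged difference at certain stopping. It rests on assumed marker levels, slopes and variances, a straight-line fall on the log scale, and the inference that the routine labs are the unnamed markers. Deaths, a second source of incomplete series, were not simulated. This is a flaw in a secondary analysis, worth correcting because the correction is cheap and should be settled before unblinding.

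**What to change.** In Section 9, for the routine injury labs only:

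- List the labs that count as tissue-injury markers.
- Replace repeated-measures ANOVA by a linear mixed model on the log scale, fitted to every recorded value at its actual time, with random intercept and slope and a treatment-by-time term.
- State the arm difference in change to 72 h as the contrast.
- Record a reason code when a lab is stopped because it is normal.

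Do not add last-value-carried-forward as a sensitivity analysis. If the marker is still falling, it pulls the 72 h change towards no effect, and in the simulations it did worse than complete cases.

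The cost is SAP wording, one code on the lab form and slightly more analysis work. The model relies on stopping depending only on recorded values, which Section 8 suggests and the reason code helps to check. No blood draw or clinical rule changes.
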